On the basis of these findings, the aim of this study is to test whether rTMS of the left DLPFC could be effective in treating CUD.

C. Study Overview

This is a between-subject double-blind, randomized, sham-controlled study with a 1:1 allocation into two parallel arms: 15 Hz, or sham rTMS stimulation. Participants will be 80

treatment-seeking patients, between the ages of 18-65, who meet diagnostic criteria for CUD (moderate to severe). Criteria for study enrollment are listed below. All participants will be informed about study procedures and will provide written informed consent prior to the experiment, in line with the Helsinki Declaration developed by the World Medical Association.

Recruitment: We aimed to recruit patients from rural and urban areas, in order to take account of possible differences in substance consumption and addiction severity. Therefore, recruitment will take place in two different cities: Rome, a large metropolitan area, and Chieti, a small city in the center of Italy, where the majority of patients will be enrolled from rural surroundings. Participants enrollment will be performed by a multidisciplinary team (physicians, psychologists), who have been trained and have extensive experience in performing the assessments included in the current study.

Inclusion criteria

- 1. Age 18 65;
- 2. Current diagnosis of cocaine use disorder (from moderate to severe), based on the Diagnostic and Statistical Manual of Mental Disorder Fifth Edition (DSM-5);
- 3. Abstinence from cocaine for at least 48 hrs.

Exclusion criteria

- Current DSM-5 diagnosis of substance use disorders other than nicotine Current DSM-V diagnosis of moderate to severe alcohol use disorders
- 2. Current DSM-5 diagnosis of schizophrenia, bipolar disorder, or other psychotic disorder;
- 3. Use in the past 4 weeks of any medication with known proconvulsant action; or current regular use of any psychotropic medications (benzodiazepines, antipsychotic medications, tricyclic antidepressants, anti-epileptics, mood stabilizers);
- 4. Any history of any clinically significant neurological disorder, including organic brain disease, epilepsy, stroke, brain lesions, multiple sclerosis, previous neurosurgery, or personal history of head trauma that resulted in loss of consciousness for > 5 minutes and retrograde amnesia for > 30 minutes;

- 5. Any personal or family history (1st degree relatives) of seizures other than febrile childhood seizures;

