 Completion time: < 5 min.
- Brief Psychiatric Rating Scale (BPRS- brief version): to assess psychiatric symptoms. Completion time: 15 min.
- Visual Analogical Scale for Food Craving (VAS food): to assess food craving.
 Completion time: ~ 5 min.
- Insomnia severity index (ISI): to evaluate sleep patterns and quality. Completion time:

 ∼ 3 min.
- Symptom Checklist-90-R (SCL-90-R): brief self-report psychometric instrument to evaluate a broad range of psychiatric symptoms and to measure the progress and outcome of psychiatric and psychological treatments. Completion time: ~ 15 min.

Executive and Cognitive Function will be assessed at baseline, at the end of continued rTMS treatment phase, at the end of rTMS follow-up phase and at the end of the no rTMS follow-up phase. Executive Function and Cognitive Assessment include:

- Frontal Assessment Battery (FAB): to assess frontal dysexecutive phenotype. Completion time: ~ 10 min.
- Eriksen Flanker Task (Flanker): to assess the ability to suppress responses that are inappropriate in a particular context. Completion time: ~ 15 min.
- Iowa Gambling Task: to assess decision-making process. Completion time: ~ 15 min.

E. Study Design

The study itself will consist of three phases.

- (1) an outpatient screening phase, during which patients will be screened to assess their eligibility to be enrolled in the study. This phase will include informed consent and randomization, and will conclude with baseline data collection.
- (2) a continued rTMS treatment phase, during which subjects will receive 20 stimulation sessions (2 daily, 5 days/week). In addition to this, participants will also attend self-help groups twice per week, as part of standard-of-treatment for CUDs.

During this phase, treatment response will be assessed by evaluating cocaine craving and consumption, psychiatric and medical symptoms and functioning.

(3) a follow-up phase of 24 weeks, which will be structured as following. During the first 12 weeks (rTMS follow-up) subjects will be asked to return to the Outpatient Clinic for an outpatient visit. During these visits, participants will undergo real or sham stimulation (two consecutive sessions per day), and will also attend self-help groups once per week.

During the following 12 weeks (no rTMS follow-up), participants will not receive TMS but behavioral and other data will be collected to observe long-term effects of rTMS.

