- Changes in CCQ score between the active rTMS and sham group, and from pre- to post treatment [baseline and after rTMS treatment: 2 weeks, 3 months, 6 months];
- Percent of negative urine samples between the active rTMS and sham group, and from pre- to post treatment [baseline and after rTMS treatment: 2 weeks, 3 months, 6 months].

Secondary aims:

- Changes in the scores on the 90 Symptoms Questionnaire (SCL-90) from pre- to post treatment [baseline and after rTMS treatment: 2 weeks, 3 months, 6 months];
- Changes in the scores of the Montgomery-Asberg Depression Scale (MADRS) from pre- to post treatment [baseline and after rTMS treatment: 2 weeks, 3 months, 6 months];
- Changes in the scores on the Hamilton Anxiety Rating Scale (HARS);

- Changes in the scores on the frontal assessment battery (FAB), and on the Flanker task from pre- to post treatment [baseline and after rTMS treatment: 2 weeks, 3 months, 6 months];
- Changes in the scores of the Iowa Gambling Task from pre- to post treatment [baseline and after rTMS treatment: 2 weeks, 3 months, 6 months];

Exploratory aims:

- DLPFC BOLD signal change in response to cocaine-related cues from baseline to each time point, and between the active and sham group;
- Changes in resting state functional connnectivity between the DLPFC and other nodes of the executive control network (ECN), from baseline to each time point, and between the active and sham group.

Statistical Analysis

Behavioral measures on each of the cognitive tasks as well as questionnaire data from each of the experimental conditions will be compared both within and between experimental groups using mixed, repeated-measures ANOVA, and linear mixed models. When assessing the statistical results from the behavioral and questionnaire data, a standard α -level of 0.05 will be used. Alpha-levels for multiple comparison follow-up tests will be corrected using an appropriate method (e.g., Bonferroni, Tukey, Scheffe).

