Safety: Participants will be presented with information about the study prior to data collection and they will be informed of their right to withdraw their information at any time, and that by taking part they are providing consent for the research team to use their anonymised data for research (including publications and other forms of dissemination) (informed consent and information sheets are attached as annexes, Italian version). Furthermore, they will provide written informed consent prior to the experiment, in line with the Helsinki Declaration developed by the World Medical Association. The research team will not include people if they

are unable to give informed consent. The Health and Human Sciences Ethics Committee at the University of Chieti approved the research before it commences.

Randomization: We aimed to recruit a total of 80 patients (40 per rTMS and 40 per sham-stimulation). The distribution will be generated randomly to allow for an equitable age and sex distribution.

Double-blind procedure: rTMS will be used with the software necessary for the operator to remain blind to the stimulation condition. Also, the software will be pre-programmed by a staff member that will not be involved in data collection and analysis. The sham condition will match the number of pulses delivered during the 15Hz session and will use the same coil placement but the intensity of stimulation will be set a 3% of the individual resting motor threshold so to ensure that the participant will feel similar scalp sensations experienced by participants receiving active rTMS, but brain tissue will not be stimulated.

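### Recruitment is split between two cities because consumption and severity may differ, but site is named in neither the randomisation text nor the primary analysis

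*Combined protocol and SAP*

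**What the plan says.** Section C (Study Overview, Recruitment) states that "recruitment will take place in two different cities: Rome, a large metropolitan area, and Chieti, a small city in the center of Italy", with most Chieti patients coming from rural surroundings. The stated reason for covering rural and urban areas is "in order to take account of possible differences in substance consumption and addiction severity". The split of the 80 patients between the cities is not given.

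The same section describes a "randomized, sham-controlled study with a 1:1 allocation into two parallel arms". The Randomization paragraph of section G gives 40 patients per arm and then one sentence on method: "The distribution will be generated randomly to allow for an equitable age and sex distribution". It mentions no strata, blocks or minimisation, for age and sex or for any other factor.

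The primary aims in section F are "Changes in CCQ score between the active rTMS and sham group, and from pre- to post treatment", and the percentage of negative urine samples, compared in the same way. The Statistical Analysis text names mixed repeated-measures ANOVA and linear mixed models, with no site term and no other covariate. The power paragraph rests on an unadjusted two-group t-test with a standardised effect of 0.65.

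**The concern.** The plan gives a reason for using two kinds of catchment area, and that reason concerns a co-primary outcome. Neither the allocation nor the analysis then uses site. With 40 patients per arm, chance alone can leave one arm with noticeably more patients from one city. If the cities do differ on craving or consumption, part of the observed arm difference in that realised trial would reflect site mix, in either direction. Even with well-balanced arms, variation between sites that a model term could remove would stay in the error variance.

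**Working it through.** **Inputs from the documents.** N = 80, 40 per arm, 1:1 (sections C and G). Two sites (section C). Standardised effect 0.65, one-tailed α = 0.05, about 30 evaluable per group (power paragraph).

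**Assumptions, not in the documents.** A 40:40 allocation with no restriction by site; n = 20, 30 or 40 patients at the smaller site; a between-site outcome difference D of 0.3 to 0.5 SD for the main range, with 0.2 and 0.8 SD as wider limits; 80% power, which the plan does not state.

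**The plan's own figure.** The normal-approximation formula gives n per group = 2 × (1.645 + 0.842)² / 0.65² = 29.3, so 30. The noncentral t-test with 30 per group, one-tailed, has power 0.800. The stated 30 per group therefore reproduces at 80% power, and nothing below changes it.

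**Chance imbalance by site.** Let X be the number of the site's n patients who fall in the active arm. X is hypergeometric (80 patients, 40 active, n drawn), and the arm difference at the site is 2X − n. The SD of the difference in site share between arms is 2 × SD(X) / 40.

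| Patients at smaller site | SD of share difference | P(differ by ≥ 4) | P(≥ 6) | P(≥ 8) |
|---|---|---|---|---|
| 20 | 9.7 points | 0.439 | 0.196 | 0.069 |
| 30 | 10.9 points | 0.489 | 0.248 | 0.105 |
| 40 | 11.3 points | 0.503 | 0.263 | 0.117 |

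Differences of 4, 6 and 8 patients are 10, 15 and 20 percentage points of an arm of 40.

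**Effect on the arm contrast.** Shift = (difference / 40) × D.

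- 6 patients, D = 0.3: 0.15 × 0.3 = 0.045 SD.
- 8 patients, D = 0.5: 0.20 × 0.5 = 0.10 SD, which is 0.10 / 0.65 = 15% of the design effect.
- Over all allocations, the SD of the shift runs from 0.097 × 0.3 = 0.03 to 0.113 × 0.5 = 0.06 SD. The sampling error of the arm difference is √(2/40) = 0.22 SD.

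**Error rate given a bad draw.** Take equal sites, 40 per arm, no site adjustment and a 20-point imbalance that favours active treatment. The one-sided error is then 1 − Φ[(1.645 × s − 0.20 × D) / 0.2236], where s = 0.2236 × √(1 + D²/4). It is 0.07 at D = 0.2, 0.11 at D = 0.5 and 0.15 at D = 0.8, against a nominal 0.05. An imbalance in the other direction lowers it.

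**Precision.** With within-site SD 1 and site share f, the SD that ignores site is √(1 + f(1 − f)D²). At D = 0.5 this is 1.023 (f = 0.25) or 1.031 (f = 0.5). Power with 30 per arm is Φ[0.65 / (SD × √(2/30)) − 1.645]:

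- with site in the model: 0.809 (normal approximation; this is the 0.800 of the t-test above);
- without site, D = 0.5: 0.793 to 0.787, a loss of about 2 points;
- without site, D = 0.2: 0.806 to 0.805;
- without site, D = 0.8: 0.769 to 0.756.

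The share of outcome variance due to site, f(1 − f)D² / (1 + f(1 − f)D²), is 1.7% to 5.9% for D = 0.3 to 0.5 and f = 0.25 to 0.5.

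**The case against.** Chance imbalance under randomisation is not bias. Over repeated allocations the type I error is kept, and the ordinary standard error already covers site variation. The shifts of 0.045 to 0.10 SD are conditional on an unlucky draw; the typical shift is small beside a sampling error of 0.22 SD. Both primary aims compare pre- with post-treatment values, so a stable difference between cities is at least partly removed. Neither D nor the site split is in the documents. Recruiting in two cities can also be read simply as a way to obtain a varied sample, which it does without any further step. All of this stands, and it limits the size of the point. It does not supply a reason to leave site out.

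Three stronger readings are tempting and not supported:

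- **That the patients are expected to differ by city.** Section C speaks only of possible differences and never calls site prognostic.
- **That site also determines background care through local self-help groups or separate treating teams.** Section E gives only frequency: "participants will also attend self-help groups twice per week, as part of standard-of-treatment for CUDs" in the treatment phase, and in the rTMS follow-up participants "will also attend self-help groups once per week". It does not say where or by whom the groups are run, and no separate team per city is described.
- **That allocation uses an unrestricted list, or is formally balanced on age and sex alone.** The Randomization paragraph states neither. What can be said is that no method is described and site is not named.

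**Conclusion.** The point holds as a low-to-moderate recommendation, with moderate confidence. Site, which the plan itself links to possible differences in a co-primary outcome, is absent from both the randomisation text and the analysis text. If allocation is not restricted by site, an imbalance of 6 or more patients at a site has a chance of roughly one in five to one in four. Its effect on the arm contrast is modest (at most about 15% of the design effect for D up to 0.5 SD), as is the power cost. Those sizes depend on the assumed site split and D. A reader should not infer that the primary comparison is biased or that the sample size is wrong: the overall type I error is kept and the 30 per group reproduces. The reason to act is that the better method costs almost nothing.

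**What to change.** - **Randomization (section G).** State the method: 1:1 allocation stratified by site (Rome, Chieti), in permuted blocks of varying size. The arm difference within a site can then be at most half the largest block. Age and sex may stay as balance factors, with the method stated, or become model covariates.
- **Statistical Analysis (section F).** Add site as a fixed effect in the primary models for craving and for consumption, so that the analysis matches the stratified allocation.

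The cost is one stratification factor, one model term and some wording. The sample size, visits and procedures stay as they are, and varying block sizes keep the next allocation hard to predict. The change cannot restore balance for patients already randomised, but the model term can still be added before unblinding.
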